Since December 18th 2019, esketamine intranasal obtained a European marketing authorization from EMEA. Thereafter, the manufacturer issued a compassionate use program (CUP) for the Netherlands before the reimbursement would be established, aiming at severely treatment resistant depressed patients (e.g. unsuccessful response to MAO-Inhibitors and/or ECT). As treatment with esketamine intranasal requires protocolized administration under strict supervision of patients in at least a day-care treatment facility, a limited number of centres will provide esketamine treatment, initially via the CUP, which, after reimbursement, was continued with new treatment centres. Current centres where esketamine intranasal spray treatments are administered: Radboudumc, Amsterdam UMC, UMC Utrecht, LUMC, GGZ Drenthe, ApareeGGZ, UMCG, Elisabeth Tweesteden Ziekenhuis, Maxima Medisch Centrum Eindhoven, Mondriaan / PsyQ Maastricht, GGZ Delfland, Antonius

ziekenhuis Nieuwegein, Parnassia Psy-Q Den Haag, Parnassia Antes, Parnassia Noord-Holland Castricum, Synaeda/GGZ Friesland, Vincent van Gogh, ProPersona, GGNet, GGZ Centraal, Reinier v Arkel, Amphia, Emergis, Rivierduinen, GGZ Noord-Holland Noord, Lentis, Spaarne gasthuis, Altrecht, Isala, Rivierenland, Ziekenhuis Groep Twente, Gelre Ziekenhuis, GGZ InGeest. These centres are collaborating on exchanging treatment protocols and clinical experience in order to increase the knowledge with this new application.

OBJECTIVES

Primary Objective: To collect pseudo-anonymized short- and long-term effectiveness and acceptability data for the treatment with esketamine intranasal in treatment resistant depressed patients treated in collaborating esketamine treatment centres in the Netherlands.

Secondary Objective(s):

[figure not shown]
To pool pseudoanonymised data of effectiveness and acceptability of esketamine intranasal from based on clinical registrations in patient's real-world health records.

To use predicted treatment response based on pooled clinical and behavioural data as pre-selection tool.

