2.4 Sample size calculation

As this is a cohort study, in which we want to use clinical data for summary purposes regarding effectiveness and acceptability, we did not perform an a priori power calculation.

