8.3 Other study parameters

The DM-TRD will be used as a continuous variable in regression and mixed model analyses. For illustrative purposes the scores of this scale can be split into tertiles (low medium and high levels of TRD).

PIT and clinical data will be combined and used to (iteratively) train machine learning algorithms, to build an optimal prediction tool for clinical decision-making: Therefore, we adopt a computational psychiatry approach, a rising field fueled by the lack of breakthroughs in psychiatric practice and inspired by advances in cognitive neuroscience and data-science. Computational psychiatry aims to improve clinical practice through mechanism- and machine-learning based predictions. Accordingly, we will use advances in computational cognitive neuroscience (PIT) and machine-learning (prediction) towards improved outcomes for TRD patients. This is timely because of evidence of clinical predictive value of PIT (Huys, 2016, Chen 2020), iSk registration for TRD and the availability of solid computational frameworks with readily employable machine-learning

algorithms, which enable us to perform predictions on the individual level within high-dimensional data.

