Following the STROBE22 guideline, we will build a model to predict response in terms of depressive symptom reduction after 4 weeks of treatment with esketamine intranasal sprays. Clinical and computational parameters from PIT (easy to administer, web-based test measuring the influence of affect on reward-driven behaviors), collected before treatment initiation in 350 TRD patients, will be used as predictors. To predict response based on multiple predictors (PIT, questionnaire, demographical, clinical data) I will follow TRIPOD(-AI) guidelines and use common machine learning procedures (i.a. support vector machine, penalized regression and tree-based approaches) with cross-validation to prevent overfitting. The best algorithm in terms of precision-recall area under the curve will be tested on a hold-out test dataset (not involved in algorithm tuning) against at least reasonable specificity (90%) for non-response, making it acceptable for clinical purposes. As external validity is very important (and often not taken into account) in translational research, we will test algorithms again through continuous data collection and assess clinical utility with common test-statistics. Test data will be used to optimize algorithms iteratively, by further hyperparameter tuning (test and tune procedure).

For each separate analysis done in this consortium, we will pre-register an analysis plan at the Open Science Framework (<https://osf.io/>)

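### Section 8.3 accepts the pre-selection tool on 90% specificity and unnamed test statistics, neither of which by itself compares using the tool with treating every eligible patient

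*Protocol*

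**What the plan says.** The intended use is stated in the Summary and again under the secondary objectives: "To use predicted treatment response based on pooled clinical and behavioural data as pre-selection tool". Section 8.3 gives the aim as "to build an optimal prediction tool for clinical decision-making".

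Section 8.3 then fixes three things about how the tool is judged:

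- **Choice of algorithm.** "The best algorithm in terms of precision-recall area under the curve will be tested on a hold-out test dataset". This ranks the candidates against each other and sets no minimum.
- **Acceptance.** The chosen algorithm is tested "against at least reasonable specificity (90%) for non-response, making it acceptable for clinical purposes". The 90% is not derived, and no minimum sensitivity goes with it.
- **Utility.** On data that continue to accrue, "we will test algorithms again through continuous data collection and assess clinical utility with common test-statistics". The statistics are not named.

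The predictors are "collected before treatment initiation in 350 TRD patients, will be used as predictors". Section 2.4 says of the study as a whole that "we did not perform an a priori power calculation". Section 8.3 also cites TRIPOD(-AI) and promises a pre-registered plan on the Open Science Framework for each analysis.

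**The concern.** Everyone in the cohort is clinically eligible for esketamine and receives it. A pre-selection tool can therefore change practice only by separating out some of these patients as unlikely to respond. Whether that helps depends on three things: how many responders are flagged for each non-responder flagged, how clinicians weigh the one against the other, and how the result compares with treating all eligible patients.

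A specificity floor speaks only to the responders. It says nothing about how many non-responders are found, how common response is, or what the weighting should be. Conventional test statistics may supply some of these parts, but the protocol names no comparator and no weighting. As the text stands, a tool could be called acceptable and useful although using it would be no better, or worse, than not using it. In a treatment-resistant population, wrongly flagging a responder is a weighty error.

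**Working it through.** The protocol contains no calculation to reproduce, because the 90% is asserted. The check asks whether a tool that meets the 90% can still fall short of treating all.

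**Inputs**

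- Specificity for non-response 90% (section 8.3). Non-response is read as the positive class, so 10% of responders are flagged.
- 350 patients (section 8.3).
- Response rate *p*: not in the protocol; assumed 0.30 to 0.60.
- Sensitivity *s* (share of non-responders flagged): not in the protocol; assumed 0.20 to 0.40, with 0.10 for random flagging.
- Threshold probability *pt* (the response probability above which one would treat): not in the protocol; left free. Write *w* = *pt*/(1 - *pt*).

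**Net benefit, with response as the event and unflagged patients treated**

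- Treat all: NB(all) = *p* - (1 - *p*)*w*. Treat none: 0.
- Tool: NB(tool) = 0.90*p* - (1 - *s*)(1 - *p*)*w*.
- Difference, tool minus treat-all: D = -0.10*p* + *s*(1 - *p*)*w*.

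**An uninformative tool.** Flag 10% of patients at random. Specificity is 90% and *s* = 0.10, so NB = 0.90*p* - 0.90(1 - *p*)*w* = 0.9 × NB(all). NB(all) is positive whenever *p* exceeds *pt*, and the random rule is then worse than treating all. At *p* = 0.50 and *pt* = 0.20 (*w* = 0.25), NB(all) = 0.50 - 0.125 = 0.375 and D = -0.0375, or -3.75 per 100 patients. In 350 patients with *p* = 0.50, it flags 0.10 × 175 = 17.5 responders and 17.5 non-responders. It still meets the only numerical acceptance criterion in section 8.3.

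**An informative tool.** Take *p* = 0.50 and *s* = 0.30.

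- At *pt* = 0.20: D = -0.05 + 0.15 × 0.25 = -0.0125, or -1.25 per 100.
- At *pt* = 0.30: D = -0.05 + 0.15 × 0.4286 = +0.0143, or +1.43 per 100.

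Sensitivity, specificity and response rate are the same in both lines. Only the weighting differs, and the sign changes.

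**Break-even.** Setting D = 0 gives *pt** = 0.10*p* / [0.10*p* + *s*(1 - *p*)].

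| *p* | *s* | Calculation | Break-even *pt* |
|---|---|---|---|
| 0.50 | 0.30 | 0.05 / (0.05 + 0.15) | 25% |
| 0.40 | 0.20 | 0.04 / (0.04 + 0.12) | 25% |
| 0.30 | 0.40 | 0.03 / (0.03 + 0.28) | 10% |
| 0.60 | 0.20 | 0.06 / (0.06 + 0.08) | 43% |

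The break-even rises with *p* and falls with *s*, so the last two rows bound the assumed range. The tool beats treating all only when the threshold probability lies above the break-even.

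The break-even is also the response probability among flagged patients, that is, 1 minus the predictive value for non-response. At *p* = 0.50 and *s* = 0.30 the predictive value is 0.15/0.20 = 75%, or one responder flagged for every three non-responders.

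**The other reading of the 90%.** If it means that 90% of non-responders are correctly classified, the share of responders flagged has no cap. Flagging 90% of patients at random would then comply, with NB = 0.10*p* - 0.10(1 - *p*)*w* = 0.1 × NB(all).

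**The case against.** A reader might infer that conventional test statistics cannot show whether the tool beats treating all. The documents do not support that. The statistics are left undefined, so it would be wrong to say that the plan confines itself to sensitivity and specificity. One common statistic, the predictive value for non-response, gives the break-even threshold directly. What is missing is the comparator and an agreed threshold range.

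A reader might also infer that the tool would do net harm. That is not shown either. The sign depends on response rate, sensitivity and threshold, and the protocol gives none of them. The 90% floor is the protocol's own safeguard and, on the natural reading, limits the responders flagged to 10%. The study is observational, and the protocol states no rule by which treatment is withheld on a prediction. In a single-arm cohort, response is not the causal effect of treatment, so net benefit computed from it cannot prove harm or benefit from withholding.

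The remaining objection is that such detail belongs in the promised pre-registered plans and is covered by the TRIPOD(-AI) reference. That would be a full answer if section 8.3 were silent. It is not: it ties clinical acceptability to 90% specificity and utility to test statistics. A later plan could add a better measure, but it would have to depart from that wording.

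**Conclusion.** The point holds in a limited form. The acceptance criterion and the utility assessment in section 8.3 do not, by themselves, support a conclusion that the tool is clinically useful. The clearest evidence needs no assumed threshold value: a random rule meets the 90% criterion and keeps only 0.9 of the net benefit of treating all whenever the response rate exceeds the threshold.

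For an informative tool the answer is open. The break-even threshold is 25% in the central example and 10% to 43% over the assumed range. These figures rest on reading non-response as the positive class, on specificity of exactly 90%, and on assumed response rates and sensitivities.

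The matter concerns an analysis listed under other study parameters and does not touch the primary endpoint. It should be put right before the prediction work is evaluated, because the remedy is nearly free and the tool is meant to guide patient selection.

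**What to change.** In section 8.3:

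- Keep the usual test statistics, and add net benefit (decision-curve analysis) of the tool against treat-all and treat-none, with 95% intervals.
- Compute it on data not used for tuning. Section 8.3 also lets test data feed back into tuning, so name the data set reserved for this step.
- Have the clinical team set the range of threshold probabilities before those data are opened.
- Report the predictive value for non-response or, equivalently, the number of responders flagged per non-responder flagged.
- Drop the inference from 90% specificity alone to clinical acceptability. Claim clinical utility only where net benefit exceeds treat-all within the pre-set range.
- State which class the 90% refers to, and state that response in a single-arm cohort is not the causal benefit of treatment.

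The cost is a change of wording and a few lines of code on predictions already made; no new data are needed. The downside is that a threshold range must be agreed in advance and that a claim of utility becomes harder to make.

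### Protocol section 8.3 contradicts itself on whether test data are used for tuning, and reserves no unused data for evaluating the re-tuned prediction model

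*Protocol*

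**What the plan says.** One paragraph of Protocol section 8.3 (Other study parameters) makes four statements in this order.

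- Several types of algorithm are developed "with cross-validation to prevent overfitting".
- The winner on precision-recall AUC "will be tested on a hold-out test dataset (not involved in algorithm tuning"). It is judged "against at least reasonable specificity (90%) for non-response, making it acceptable for clinical purposes".
- For external validity, "we will test algorithms again through continuous data collection".
- "Test data will be used to optimize algorithms iteratively, by further hyperparameter tuning (test and tune procedure").

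The paragraph does not define the test data in the last statement. It does not say when the model is locked, which patients will be used to assess a re-tuned version, or which performance estimate will be reported. It commits to TRIPOD(-AI) and to a pre-registered plan on the Open Science Framework for each analysis.

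**The concern.** A validation figure is honest only if the data behind it played no part in choosing the model. Once results on a test set steer hyperparameters, that set belongs to development, and its performance figure contains selection noise. The second and fourth statements of the paragraph therefore conflict if the test data include the hold-out. If they mean only later patients, those patients were brought in to show external validity and lose that role for the version tuned on them.

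This is more than detail left to an analysis plan. The protocol states a procedure, and a later plan that followed it faithfully would inherit the problem. What is at stake is the objective of using predicted response as a pre-selection tool. The section treats 90% specificity as what makes the tool clinically acceptable, so optimism could carry a model over that line when its true performance falls short.

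**Working it through.** **Reading the text.** There is no plan figure to reproduce. The number 350 enters only as "collected before treatment initiation in 350 TRD patients, will be used as predictors", section 2.4 states that "we did not perform an a priori power calculation", and 90% is a target. The possible meanings of the fourth statement are:

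- *The hold-out:* this contradicts the second statement, and the hold-out cannot validate the re-tuned model.
- *Later patients only:* there is no contradiction, but those patients cannot validate the version tuned on them. The hold-out could be revisited, but the text does not plan this, and it would stay clean only if no earlier hold-out result had guided a tuning round.
- *Both:* both problems apply.

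On every reading, the evaluation of the re-tuned version on unused patients is missing.

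**Illustration of size.** All inputs except 350 and 90% are assumptions.

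- Hold-out of 20% to 30% of 350: 0.20 × 350 = 70; 0.30 × 350 = 105.
- 50% non-response, so the class on which specificity is computed has 35 or 52 patients.
- K configurations of identical true discrimination are compared on the same test patients. Score of configuration k in patient i: s = √ρ·z_i + √(1−ρ)·e_ki + d·y_i, with z and e standard normal, y the outcome class, d = √2·Φ⁻¹(true AUC), and ρ = 0.5 or 0.9.
- The best configuration on those patients is kept. Optimism is its mean apparent value minus the true AUC. For PR-AUC it is minus the mean of a single unselected configuration. There were 1,500 runs per setting.

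AUC optimism (true AUC 0.50 / 0.70):

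| Test patients | ρ | K = 1 | K = 5 | K = 20 | K = 50 |
|---|---|---|---|---|---|
| 70 | 0.5 | −0.001 / 0.000 | 0.059 / 0.053 | 0.093 / 0.082 | 0.112 / 0.101 |
| 70 | 0.9 | 0.001 / 0.002 | 0.029 / 0.024 | 0.042 / 0.039 | 0.054 / 0.049 |
| 105 | 0.5 | 0.001 / 0.000 | 0.047 / 0.042 | 0.076 / 0.067 | 0.093 / 0.082 |
| 105 | 0.9 | −0.001 / −0.002 | 0.022 / 0.017 | 0.035 / 0.033 | 0.043 / 0.039 |

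For K from 5 to 50 the range is 0.017 to 0.112. For PR-AUC, the protocol's own selection metric, it is 0.021 to 0.107. With one evaluation on unused data (K = 1), AUC optimism is zero to within simulation error.

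**The 90% criterion.** Suppose true specificity is 0.85. Reaching 90% needs at least 32 of 35 (0.9 × 35 = 31.5) or 47 of 52 (0.9 × 52 = 46.8).

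- One look, exact binomial: P(X ≥ 32 | 35, 0.85) = 0.209; P(X ≥ 47 | 52, 0.85) = 0.188.
- At least one of 5 configurations passes (4,000 runs, ρ = 0.5 / 0.9): 0.589 / 0.439 with 35 patients; 0.559 / 0.405 with 52.
- At least one of 10: 0.746 / 0.516 with 35; 0.720 / 0.487 with 52.

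Even a clean result near 90% is imprecise at these sizes. The 95% Clopper-Pearson interval is 0.77 to 0.98 for 32/35 and 0.79 to 0.97 for 47/52.

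**The case against.** The text never says outright that the hold-out is fed back. The re-tuning statement directly follows the one on newly accruing patients and can be read as ordinary model updating on them. The same section also speaks of training iteratively. On that reading the hold-out promise is intact. TRIPOD(-AI) and the pre-registered plan give the sponsor a place to settle the matter. The size cannot be derived from the protocol. The simulation gives all configurations the same true performance, so all of the apparent gain is noise, whereas in practice part of a tuning gain may be real. Finally, this is the last-listed secondary objective, and the tool does not appear in this cohort's eligibility criteria.

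Most of this stands. A reader might infer that the hold-out is certainly consumed, that no untouched data remain, and that the reported accuracy must therefore be biased. The protocol does not support that. Which data are re-used is unspecified, continued accrual can supply unused patients, and a hold-out result taken before any feedback is clean.

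Two things remain. The wording conflicts on its face, since the hold-out is the only dataset the paragraph names as a test dataset. And even the favourable reading plans no evaluation of the re-tuned version on patients it has not used. Pre-registration could repair this but does not correct the current text.

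**Conclusion.** The point holds in a limited form. Section 8.3 contradicts itself on whether test data enter tuning, does not say which test data are meant, and reserves no unused data for the re-tuned model. Performance reported on re-used test data would be optimistic. Whether the published figure is optimistic depends on which estimate is reported, and the protocol leaves that open.

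The size is illustrative only: about 0.02 to 0.11 on AUC. For a configuration with true specificity 0.85, the chance of an apparent pass at 90% rises from about 0.19–0.21 with one look to 0.40–0.59 for the best of 5 and 0.49–0.75 for the best of 10. These figures rest on the assumed split, non-response rate, number of configurations, score correlation and equal true performance, and on repeated use of one test set. The MADRS primary endpoint is unaffected.

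**What to change.** Replace the test-and-tune sentence in section 8.3 with text to this effect:

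- All tuning, algorithm choice and threshold setting use development data only.
- The model is then frozen and evaluated once on the hold-out, and that result is reported as obtained.
- If the model is later updated, the test data used for the update become development data. The updated version is evaluated only on patients enrolled after it was frozen.
- Results are reported by model version.

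Mirror this in the pre-registered plan. Whether to nest the cross-validation and where to fit the PIT parameters can be left to that plan.

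The cost is a wording change, with no extra measurements and no accrual beyond what is already planned. The reported accuracy may be somewhat lower, and each updated version has no validation result until enough later patients have been followed for the 4-week outcome.

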8.4 Interim analysis

N/A

9. ETHICAL CONSIDERATIONS

9.1 Regulation statement

N/A

9.2 Recruitment and consent

Recruitment of the project will be via the regular referrals to the Radboudumc Department of Psychiatry, which has a role as referral centre for TRD, or other participating centres. Possibility of esketamine intranasal treatment will be communicated with colleagues and our network.

To all patients the purpose of this data collection will be explained with both written and oral information and informed consent for data collection and (pseudo-anonymised) pooling will be obtained and stored.

9.3 Objection by minors or incapacitated subjects (if applicable)

N/A

9.4 Benefits and risks assessment, group relatedness

N/A. Treatment and assessment of risk and benefits will be done from a clinical/treatment perspective.

9.5 Compensation for injury

N/A

9.6 Incentives (if applicable)

N/A

10. ADMINISTRATIVE ASPECTS, MONITORING AND PUBLICATION

10.1 Handling and storage of data and documents

All data (questionnaires and evaluations) will be primarily recorded in the patient's health record. Only after informed consent data will be abstracted and anonymised by a study-number. For the second aim of this project the study-number will only disclose the treating hospital where the patient was treated, no referral to initials or birth-date of participants will be made in the study-number. The key between the study-number and the patient will be stored at the hospital (at a secured directory only accessible to the local physician) and will not be shared outside the hospital.

10.2 Monitoring and Quality Assurance

N/A

10.3 Amendments

Current versions 2.3 and 2.4 contains amendments.

10.4 Annual progress report

N/A

10.5 Temporary halt and (prematurely) end of study report

N/A

10.6 Public disclosure and publication policy

Summary reports for the hospital and internal evaluations will be made. For the second aim of this project we will aim to publish a case-series/cohort-report of patients treated with intranasal esketamine and explore effectiveness and acceptability of this new treatment in relation to the level of TRD when the treatment was initiated.

